#### **IV. SUBJECT POPULATION**

##### **A. Number of Subjects**

We plan to prospectively enroll 40 patients in this study.

##### **B. Inclusion Criteria**

Surgical defect on the lower extremity left to heal by secondary intention. There is no minimum size for the wound. Women of child-bearing potential must be using medically-accepted contraceptive measures in order to participate in the study. Patients must be able to complete all study-related visits as scheduled. Maximum size of the wound is 5cm x 5cm.

##### **C. Exclusion Criteria**

Any history of porphyria, photosensitive cutaneous eruptions, diabetes mellitus, history of venous insufficiency, or known history of peripheral arterial disease as defined by an ABI < 0.8, any ointments or creams containing known photosensitizers such as coumarins or porphyrins should be discontinued for 2 weeks prior, any systemic or topical retinoids, especially isotretinoin, in the past 6 months, current pregnancy or lactating, any patient with a history of metastatic cancer. Individuals under the age of 18 years will also be excluded from the study.

#### **V. STUDY PROCEDURES**

Those patients who have a surgical defect on the lower extremity that will be left to heal by secondary intention and are willing to participate in the study will be consented and enrolled in the study.

The following information will be recorded in a prospective fashion: Patient's age, gender, race/ethnicity, type of skin cancer removed, clinical size of lesion (mm) and size of resulting defect following surgery. It will also be recorded to what group, treatment with LED and standard wound care versus sham light treatment and standard wound care with no LED. Clinical photos of the lesion will also be taken.

The experimental group will receive treatment with the light emitting diode (LED) for 20 minutes of exposure at an intensity of 105 mW/cm^2 for a total of 126 J/cm^2, over the wound site. The LED emits light at wavelengths of 633 nm and 830 nm at fluences of 126 and 66 J/cm^2. This study will only utilize the 633 nm wavelength. The control group will receive sham light treatment for 20 minutes duration and standard of care for second intention healing without the LED treatment. This includes maintenance of a clean and moist wound environment. Patients will keep the wound covered with an occlusive bandage and will perform daily dressing changes. Daily gentle cleansing with soap and water and the application of antibacterial ointment as needed for wound hydration will be the recommended standard of care for both treatment and control groups.

## **VI. ADVERSE EVENTS**

The patients enrolled in the study will be treated with the standard of care for lower extremity wounds following surgery. There are no potential economic/financial, legal, psychological, social or other risks to which research participants may be exposed as a result of their participation in this research. Minor physical risks such as bleeding and infection are involved with the standard of care procedure. If a wound infection occurs the patient will be started on appropriate antibiotic therapy.

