## **III. STUDY PLAN**

Patients will be recruited from patients at the University of Miami Miller School of Medicine Mohs/Laser Unit. On the day of surgery and wound defect creation (day 0), patients will be informed of the study, and given the option of participating. If he or she decides to participate, the patient will be randomized into one of two groups in blocks of two by coin flip. The patient will remain blinded to the outcome of randomization. The experimental group will receive treatment with the light emitting diode (LED) for one session lasting 20 minutes of exposure at an intensity of 105 mW/cm^2 for a total of 126 J/cm^2 over the wound site. The LED emits light at wavelengths of 633 nm and 830 nm at fluences of 126 and 66 J/cm^2. This study will only utilize the 633 nm wavelength. The control group will receive sham light treatment for 20 minutes with standard of care for second intention healing and no LED treatment. In this case, a sham light treatment refers to regular light (not LED) exposure for 20 minutes. The sham light comes from the same device as the treatment light (Omnilux machine) however, this light has no anticipated effects on wound healing and is used simply to reduce the amount of bias that sometimes complicates the results of these studies. There is no added risk or benefit for the patients in the control group exposed to the sham light.

On day 0 the patients will be informed of the study and randomized into one of two groups by coin flip to either the experimental or control group. The patients will be blinded to which group they have been randomized too. Group 1 is the control group, which will receive sham light treatment and standard of care for lower extremity wounds. Group 2 represents the experimental group, which will receive LED treatment plus standard of care. The experimental group will receive treatment with the light emitting diode (LED) at 633 nm at one session lasting 20 minutes of exposure at an intensity of 105 mW/cm^2 for a total of 126 J/cm^2 over the wound defect, one week after wound creation (+/- 3 days). The control group will receive no LED treatment, however they will be exposed to a sham light for the duration of 20 minutes as well as receive standard of care for their lower extremity wound. Treatment will occur at one-week intervals (+/- 3 days) for a total

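### No recording or by-arm tabulation of harms is specified, and the statement attributing no risk to participation sits poorly with the photosensitivity exclusions

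*Combined protocol and SAP*

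**What the plan says.** **Risk.** Section VI (Adverse Events) states: "There are no potential economic/financial, legal, psychological, social or other risks to which research participants may be exposed as a result of their participation". It then says "Minor physical risks such as bleeding and infection are involved with the standard of care procedure", so the physical risks it names are placed with usual care and not with the light. Section III says of the sham arm: "There is no added risk or benefit for the patients in the control group exposed to the sham light". It makes no matching statement for the LED arm.

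**Eligibility.** Section IV.C excludes "Any history of porphyria, photosensitive cutaneous eruptions" and says that creams or ointments containing known photosensitizers "should be discontinued for 2 weeks prior". It does not say what the two weeks precede.

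**Data.** Section V introduces its data list with "The following information will be recorded in a prospective fashion" and names "Patient's age, gender, race/ethnicity, type of skin cancer removed, clinical size of lesion (mm) and size of resulting defect following surgery", followed by treatment group and photographs. Section III adds wound length, width and depth, and photographs before and after each session that blinded dermatologists will evaluate.

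**Handling of harms.** The one provision is in Section VI: "If a wound infection occurs the patient will be started on appropriate antibiotic therapy". Section VII discusses only comparisons of wound size and healing.

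**The concern.** Two things do not fit together. The risk statement attributes nothing to taking part, while the eligibility rules screen out people in whom light exposure could plausibly provoke a reaction. In addition, the section headed Adverse Events neither defines adverse events nor says that any will be recorded, graded or compared, and no other section does so.

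The first consequence is for safety. A device is applied four times to open surgical wounds, and the report would have no planned count of reactions or infections in either arm. Data not collected at the visit cannot be reliably reconstructed at analysis.

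The second is for efficacy. Infection and its treatment can plausibly affect how fast a wound closes. With about 20 patients per arm, a few infections concentrated in one arm could shift the healing comparison, and nobody could check afterwards whether that had happened.

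**Working it through.** The documents give no adverse event rate, safety endpoint or safety sample size, so there is no stated figure to reproduce. The check is mainly a comparison of sections. The arithmetic shows what recording would and would not deliver.

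**1. Is any harm planned to be recorded?**

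| Place | Content | Harm item specified? |
|---|---|---|
| Section III | wound dimensions, photographs, closure follow-up | no |
| Section V | demographics, tumour type, lesion and defect size, group, photographs | no |
| Section VI | infection is to be treated | treatment only |
| Section VII | wound size and healing comparisons | no |

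**2. Does the risk statement agree with eligibility?** Section VI assigns no risk to participation. The porphyria, photosensitive-eruption and photosensitizer rules in IV.C are most naturally read as guarding against a light reaction. The retinoid rule has no stated purpose, so nothing is inferred from it.

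**3. The two-week wording.** Section III informs and randomizes patients on day 0 and gives the first session one week later, +/- 3 days: 7 - 3 = day 4 to 7 + 3 = day 10. If the two weeks precede the first session and a user stops only on day 0, 4 to 10 days are available against 14. If the wording is a screening rule (no use in the two weeks before enrolment), there is no conflict. The text does not say which is meant.

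**4. What recording would deliver.** Section IV.A plans 40 patients. Section III describes two groups in blocks of two, so 40 / 2 = 20 per arm (inferred). With no events among n patients, the exact 95% upper limit is 1 - 0.05^(1/n) one-sided and 1 - 0.025^(1/n) two-sided:

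| n | one-sided | two-sided |
|---|---|---|
| 20 | 13.9% | 16.8% |
| 18 | 15.3% | 18.5% |
| 15 | 18.1% | 21.8% |

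The rows for 18 and 15 show the effect of losing patients.

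The chance of seeing at least one event among 20 is 1 - (1 - p)^20. For assumed true rates of 1%, 5% and 10% this is 18%, 64% and 88%.

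For a comparison of 20 with 20 by two-sided Fisher exact test, 4/20 against 0/20 gives p = 0.106 and 5/20 against 0/20 gives p = 0.047. At the 0.05 level, power is about 17% for assumed infection rates of 5% and 20%, and about 45% for 5% and 30%.

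**The case against.** Several stronger readings are tempting, and the documents do not support them.

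- **That nothing would be captured.** The Section V list is not exhaustive: it also omits the weekly wound measurements that Section III plainly requires. Photographs before and after each session could show a visible skin reaction, and an infection must be noticed before it can be treated. This stands. What is missing is a specified, systematic recording and a tabulation by arm.
- **That the protocol denies all risk.** It does not. It names bleeding and infection and assigns them to usual care. The accurate statement is that it attributes no risk to participation.
- **That the exclusions prove the light is harmful.** IV.C gives no rationale, and the same paragraph excludes diabetes and vascular disease. Excluding susceptible patients is itself mitigation, so a low-risk statement about those who remain is not a strict contradiction. Low risk is still not the same as no risk, so the tension remains.
- **That the two-week rule cannot be met.** That depends on an anchor date the text does not give. Only the ambiguity is established.
- **That eye symptoms were overlooked.** Nothing in the documents mentions the eyes, so the point does not rest on them.

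The consent pages are not available and may describe risks. Disclosure there would not by itself create event recording.

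It can also be said that 40 patients are too few to compare harms. As a statement about testing, that is right. It does not argue against counting.

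**Conclusion.** The point holds in this form: no section specifies recording or tabulating harms, so the trial as written would yield no systematic safety data by arm and no means of examining infection as an influence on healing. The risk statement in Section VI also needs to be reconciled with the photosensitivity rules in IV.C, and the two-week wording needs an anchor date.

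The gain from correction is real but modest. With an inferred 20 per arm and complete recording, an arm free of events would be compatible with true rates up to 13.9% (one-sided) or 16.8% (two-sided). Five events against none would be needed before a Fisher test fell below 0.05. The data would support descriptive counts, not a safety comparison. The healing comparison can still be run without the change. The conclusion rests on the available text, with consent pages absent.

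**What to change.** 1. At each weekly visit already scheduled, in both arms, record light-related skin reaction, wound infection, bleeding and antibiotic start, with dates and a short definition of each.
2. Tabulate the number of patients with each event by arm, with exact binomial confidence intervals. State in Section VII that this is descriptive. Because infection occurs after randomization, any look at its relation to healing should be labelled exploratory and should not replace the randomized comparison.
3. Reconcile the risk statement in Section VI with the exclusions in IV.C.
4. State what the two weeks in IV.C precede, and reconcile that with day-0 enrolment and a first session at one week +/- 3 days. Which clinical rule applies is for the sponsor and investigator to decide.

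The cost is a few form fields, one table and a less favourable risk statement. No extra visits or patients are needed.

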## **VII. STATISTICAL CONSIDERATIONS**

This will depend on whether we want to measure a change between the experimental and control group at particular time intervals and between groups (ANCOVA) OR do we just want to measure the difference between the control and experimental groups at particular time periods (t test). If we just do a t test, then we will not be able to make intragroup comparisons, but it will be very easy to analyze, yet still determine if the experimental group accelerates wound healing in comparison to the control group. In addition, we should probably run an unpaired t test at baseline to make sure no statistically significant difference exists in wound

size between the experimental and control groups, otherwise it could confound our results one way or the other.

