of 4 treatments for both the experimental and control/sham groups. The wounds will be created as a result of Mohs micrographic surgery or surgical excision, and left to heal by secondary intention. An Aranz silhouette camera will be used with a measurement stick on the picture. Changes from the baseline wound (including length and width) will be measured along with wound depth. These two parameters will be compared at the 1 week, 2 week 3 week, and 4-week treatment (or sham treatment) visits. After the 4th and final treatment with the LED or sham light, the patients will be followed at 1-week intervals (+/- 3 days) until the wound has closed or for a maximum of 3 months, whichever occurs first. Once the wound has closed, patients will be evaluated a final time, 1 week after wound closure to ensure that complete wound healing has indeed occurred. After this final wound evaluation, the patient's commitment required for this study will end and regular follow-up with dermatology will resume outside the scope of this study.

The clinical photographs taken before and after either LED or sham light treatment at each study visit will be evaluated by blinded assessor(s) who are board-certified dermatologist(s).

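### Section VII commits to no analysis, weighs ANCOVA against a t test on a mistaken criterion, and plans no adjustment for starting wound size; the power cost is real but conditional

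*Combined protocol and SAP*

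**What the plan says.** Section VII (Statistical Considerations) is the whole statistical plan. It poses a question and does not answer it. The analysis will depend on whether the investigators want to look at change (ANCOVA) "OR do we just want to measure the difference between the control and experimental groups at particular time periods (t test"). The trade-off it offers is this: "If we just do a t test, then we will not be able to make intragroup comparisons, but it will be very easy to analyze". It adds that an unpaired t test of wound size at baseline should probably be run, because a difference could confound the results. It does not say what follows if that test is significant.

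Other sections bear on the choice:

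- Section IV.B on wound size: "There is no minimum size for the wound", and "Maximum size of the wound is 5cm x 5cm".
- Section V records the "size of resulting defect following surgery".
- Section III on the outcome: "Changes from the baseline wound (including length and width) will be measured along with wound depth". Comparisons are planned at the visits at weeks 1, 2, 3 and 4. No scale (absolute, percentage, area or diameter) is given, and no visit is primary.
- Section IV.A: "We plan to prospectively enroll 40 patients in this study". Section III has patients "randomized into one of two groups in blocks of two by coin flip", which implies 20 per arm.

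No alpha, power, effect size, SD or correlation is given anywhere.

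**The concern.** There are three linked problems.

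1. **No method is chosen.** A result from either test could not be called prespecified. If the choice came after the data were seen, there would be two chances of a significant result at each visit.
2. **The criterion is mistaken.** ANCOVA is a between-arm comparison adjusted for a baseline covariate; it is not a device for within-arm comparisons. Nor does within-arm shrinkage bear on efficacy, because wounds in both arms are expected to heal. Adjustment for starting size, which is the real reason to prefer ANCOVA here, is never mentioned.
3. **Starting size is left unadjusted under the easier option.** With a wide eligible range and about 20 patients per arm, size at a later visit may depend heavily on size at the start. That variation inflates the standard error, and a chance imbalance moves the estimate. The baseline significance test corrects neither.

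With 40 patients there is little precision to spare.

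**Working it through.** **Inputs.** From the documents: 40 patients in blocks of two, so n = 20 per arm. Assumed, because the documents are silent: two-sided alpha 0.05, 80% power, no dropout, and a baseline-outcome correlation ρ varied over a range. The figure of 40 cannot be reproduced, since no design inputs are given. The check is therefore what 20 per arm can detect.

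**Unadjusted t test.** Noncentral t, df = 38, noncentrality d × √(n/2) = d × 3.162. Power reaches 80% at d = 0.909 SD.

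**ANCOVA.** Residual SD = SD × √(1 − ρ²), df = 37. With one degree of freedom fewer, the detectable effect before scaling is 0.910 SD, so the detectable effect is 0.910 × √(1 − ρ²). The last column is 40 × (1 − ρ²), the number of patients with which ANCOVA would match the t test on 40.

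| ρ | √(1 − ρ²) | ANCOVA detects (SD) | t-test power at that effect | Equivalent patients |
|---|---|---|---|---|
| 0.5 | 0.866 | 0.79 | 68% | 30 |
| 0.7 | 0.714 | 0.65 | 52% | 20 |
| 0.8 | 0.600 | 0.55 | 39% | 14 |

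At ρ = 0.3 the gap is small: 0.87 SD against 0.91 SD.

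**The baseline test as a safeguard.** With 20 per arm it is non-significant for any imbalance below 2.024 × √(2/20) = 0.64 SD. At ρ = 0.7, an imbalance of that size shifts an unadjusted outcome by 0.7 × 0.64 = 0.45 SD with no treatment effect at all. The check can pass while a material imbalance remains.

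**Cost of an open choice.** Under the null at a single visit (40,000 simulated trials, normal data), counting a trial as positive if either test is significant gives a false-positive rate of about 7%, 8%, 9% and 9% at ρ = 0.5, 0.7, 0.8 and 0.9. Each test used alone stays at 5%.

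**How far the power loss depends on what is not stated.** These are illustrative simulations, 20 per arm, and every healing assumption is an assumption.

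- *Raw area at week 4, proportional healing.* Control wounds keep about 45% of their area and treated wounds 0.65 times that. With diameters spread over 0.5 to 5 cm and low noise (SD 0.3 on the log scale), the t test has 28% power and ANCOVA on the same area 91%. With diameters of 1.5 to 2.5 cm and high noise (SD 0.8), the figures are 29% and 32%.
- *Linear change.* Diameters 0.5 to 5 cm, shrinkage 0.25 or 0.35 cm/week with a coefficient of variation of 30%, LED 50% faster. A t test on change in diameter against ANCOVA on square-root area gives 55% against 58% and 54% against 64% (10% error on diameter), or 79% against 81% and 65% against 76% (10% error on area). The gap is 2 to 11 percentage points.

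**The case against.** The strongest reply is that the t test may not be on raw wound size. Section III speaks of changes from baseline. If baseline and follow-up SDs are equal, a t test on change detects 0.909 × √(2(1 − ρ)), which is 0.70 SD at ρ = 0.7 and 0.575 SD at ρ = 0.8, close to ANCOVA's 0.65 and 0.55. The linear-change simulations point the same way. This stands, and it makes the loss conditional. It does not remove the point. Section VII ties change to ANCOVA and a difference at a time period to the t test, which favours the raw-size reading. A t test on absolute change in area did not help when sizes spanned the eligible range (8% to 21% power). Percentage change recovered most of the loss only if healing is proportional.

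Three stronger readings are tempting, and the documents do not support them:

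- *That the t test mostly measures starting size.* For more than half the outcome variance to come from starting size, ρ must exceed about 0.71. Simulated raw area reached 0.71 to 0.98 when sizes spanned the range, but 0.40 to 0.83 when diameters were 1.5 to 2.5 cm. Section IV.B gives limits, not a distribution.
- *That the t test is biased by starting size.* Under randomization a prespecified t test keeps its 5% error rate. The harm is lost precision and chance imbalance in a single trial.
- *That the choice will be made after the data are seen.* Section VII does not say when it will be made, so the inflated error rate is a risk and not a stated intention.

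The authors also recognise that starting size matters. Their remedy is weak, but the instinct is right.

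**Conclusion.** The point holds in this form. Three things are certain from the text: no analysis is chosen, the stated criterion is not the relevant one, and adjustment for starting size is not planned although the size is collected.

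The size of the power loss is conditional. The figures of 0.91 SD against 0.79, 0.65 or 0.55 SD rest on two-sided 0.05, 80% power, 20 per arm and correlations of 0.5, 0.7 or 0.8, none of which the documents confirm. The loss is large if enrolled wounds span the permitted range and raw size is compared. It can be negligible if wounds are alike or if linear change is analysed. Since adjustment costs almost nothing and the baseline size is already recorded, there is no good reason to leave the matter to chance.

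**What to change.** Replace Section VII with one primary analysis, fixed before unblinding:

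- ANCOVA of wound size at one named visit (for example week 4) on arm, two-sided 0.05.
- Covariate: wound size before the first treatment. State whether this is the day-0 defect or the week-1 measurement taken before the first session, since Section III does not define the baseline.
- One stated scale for outcome and covariate, for example square-root area, with closed wounds entered as zero.
- Report the adjusted difference with a 95% confidence interval. Label the other visits and wound depth as secondary.

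Delete the t-test option, the baseline significance test as a safeguard, and within-group comparison as evidence of efficacy. Baseline size can still be described by arm.

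The cost is a few lines of text and code, with no new patients, visits or measurements. The one downside is a floor from closed wounds: in the linear-shrinkage scenario above, 15% to 26% of wounds were closed at week 4. A sensitivity analysis, such as a rank-based ANCOVA, should check that the conclusion does not depend on it.
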